Studies have shown that the oral health quality of life (OHQoL) is impacted by orthodontic treatment. After orthodontic treatment, studies have shown a significant improvement in OHQoL compared to baseline measures.^{44,45} However, during orthodontic treatment, OHQoL reduces significantly, as has been shown in younger patients.⁴⁶ Motivation measures related to self-empowerment and participation in treatment have been shown to improve the overall OHQoL in schoolchildren.⁴⁷ Limited studies are available regarding the OHQoL during orthodontic treatment and further studies are needed to determine which factors contribute to improving the overall experience for patients successfully completing orthodontic nonextraction treatment with tooth movement .

Study Rationale

Currently, orthodontic treatment typically lasts approximately 2 years. There are a number of advantages for reducing the duration of treatment, including reducing the potential risk of caries², root resorption³ and for minimizing patient “burn out” from prolonged treatment.

While some evidence does exist that vibration may accelerate the speed of tooth movement, the biological mechanism is still unknown. Identification of specific factors involved in tooth movement that are further stimulated by vibration would help to understand the mechanisms involved as well as discover possible biologic targets which could be utilized or modified to maximize the benefits of vibration treatment.

The purpose of this study is to identify novel biological factors that are expressed in patients undergoing orthodontic tooth movement in conjunction with vibration appliance therapy.

Outcome Assessments

- *Primary outcome:* Changes in the expression of salivary biomarkers of bone remodeling
- *Secondary outcomes:* Changes in 1) tooth mobility, 2) change in alignment 3) changes in pain and OHQoL

Hypotheses, aims and objectives

Scientific Hypotheses

- 1) The expression of biological markers of bone remodeling are increased in combined vibration-fixed appliance treatment.
- 2) The degree of tooth mobility is increased in patients undergoing combined vibration-fixed appliance treatment compared to orthodontic treatment alone.
- 3) The percent change in alignment is greater in patients undergoing combined vibration-fixed appliance treatment compared to controls during the first 6 months of treatment.

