- 4) The orthodontic treatment pain will be reduced in patients undergoing combined treatment with a vibration appliance compared to controls.

General Objectives

Few studies exist examining the effect of vibration appliances on the rate of orthodontic tooth movement in patients. Furthermore, there is a great need to better understand the biological mechanisms by which vibration treatment may enhance tooth movement. *The primary objective of this study is to identify potential factors involved in bone remodeling which may be regulated during fixed appliance treatment in conjunction with vibration therapy.*

Specific Aims

[figure not shown]
- 1) To determine if combined vibration-fixed appliance treatment alters the expression of specific bone remodeling factors in saliva compared to fixed orthodontic treatment alone.
- 2) To further elucidate the role of vibration treatment on the degree of tooth mobility during fixed appliance treatment compared to control.
- 3) To determine if combined vibration-fixed appliance treatment increases the speed of orthodontic tooth movement during the alignment phase of treatment.
- 4) To evaluate the role of vibration treatment in the control of pain in patients undergoing orthodontic treatment.

Study Design and Screening Procedures

Study Design: Randomized controlled clinical trial:

N=40 @ UCHC Orthodontic Clinic, enrolled pre-bonding

10 Randomized to each Arm

Screening & Recruitment Procedures

Approximately 600 patients begin treatment every year in the University of Connecticut Orthodontic Clinic. The pilot project aim is to recruit a total of 40 patients, with 20 male and 20 female subjects, equally divided between control and vibration groups (above).. Based on the projected starts, we anticipate meeting the recruitment goals during the first 12 months of the study.

Prospective subjects will be screened for this study after completing all the usual initial screening procedures for patients in the University of Connecticut Orthodontic Clinic with their appointed primary orthodontic provider. The primary orthodontic provider will determine if the adult patient is likely to qualify (pre-screen) for the study based on the inclusion/exclusion criteria. The initial clinical indicators of eligibility evaluated during the pre-screen are a healthy patient undergoing non-extraction treatment with good oral hygiene. Male and female subjects of all ethnicities will be included if between the ages of 15-35 years of age.

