If the prospective adult patient meets the initial criteria, the orthodontic provider will notify the study coordinator and PI to screen the patient's existing dental records, including screening forms, models and/or radiographs for confirmation of likely eligibility for participation in the study.

When children ages 15-17 are considered for pre-screen, the provider will first obtain permission from one parent and then from the patient prospect prior to determining eligibility from the screening of existing records. If the child passes screening, the parent would be first approached by the provider about interest in participation, before also approaching the child and making a referral to the PI or Study Coordinator.

Enrollment

After the primary orthodontic provider pre-screens and identifies an interested potential subject for the study coordinator, the study coordinator will meet to discuss the study with the subject at the next appointed visit, typically the Orthodontic records appointment, at least 1 week prior to band bonding. Prior to conducting consent, the study coordinator will confirm the patient's is eligibility for the study based on review of the patient's clinical chart and the following inclusion/exclusion criteria:

Inclusion Criteria	Exclusion Criteria
Healthy, non-smoker with no systemic medical conditions and no routine medications	Patients that require extractions as part of the orthodontic plan
15 to 35 years of age at the time of bonding	Smoking or excessive alcohol consumption
Non-extraction treatment plan or no extractions required in the first 6 months of treatment	Patients with edentulous areas
At least 5mm of crowding in the mandibular arch	Evidence of periodontal disease (any pocket depths more than 4mm)
Full-complement dentition 1 st molar to 1 st molar	Use of anti-inflammatory drugs within 2 days of bonding
Good oral hygiene	Active oral lesions (ulcerations, sores, mucositis, etc.)
	Uncontrolled diabetes
	Dentofacial deformities (cleft palate, hemifacial microsomia, etc.)
	Subjects routinely taking any of the following medications: Corticosteroids (including for asthma) Bisphosphonates Anti-inflammatories Nicotine Patch Estrogen Opioids Growth Hormone Relaxin Anti-coagulants
	Disease that could affect bone metabolism: Parathyroid or thyroid dysfunction Osteoporosis, osteomalacia Vitamin D deficiency Fibrous dysplasia Paget's Disease Multiple Myeloma Osteogenesis Imperfecta History of Bone Metastasis

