Two blinded clinical evaluators will assess the rate of alignment of the lower incisors for both groups. Analyses of dental casts will be done on the mandibular cast using a method based on Little's irregularity index. Little's irregularity index was developed to assess amount of anterior tooth displacement from canine to canine (see Cast Irregularity Data Collection Form). Contact displacement will be measured in millimeters around the arch from canine to canine. Irregularity will be measured on models from each of the four time points and be evaluated based on percentage change over the 6-month evaluation period.

Orthodontic Pain Assessment

Subjects will be given a pain diary on the baseline (T0), visits T1 & T2 to record the level of orthodontic pain each evening for the first 7 days after each study visit. The degree of pain will be assessed using a Visual Analog Scale (VAS) ranging from 1 (least pain) to 10 (highest pain)⁵⁴. In addition, patients will report if the pain is constant or only present on biting/chewing⁵⁵. The subjects will return the completed diary to the next visit to be collected by the study coordinator and kept in the study record.

Oral Health Quality of Life (OHQoL)

To assess the impact of the vibration appliance on the overall oral health quality of life of the subject, subjects will be given an Oral Health Impact Profile (OHIP-14) questionnaire⁵⁶. The OHIP-14 consists of 14 questions divided into specific dimensions including functional limitation, physical pain, psychological discomfort, physical disability, psychological and social disability and overall life handicap from orthodontic treatment with or without the vibration appliance. The OHIP-14 (exhibit below) will be administered at each study visit and the profile changes will be compared across time points in data analyses.

OHIP-14 Questionnaire:

Dimension	Question	Weight
Functional Limitation	Have you had trouble pronouncing any words because of problems with your teeth or mouth?	0.51
	Have you felt that your sense of taste has worsened because of problems with your teeth or mouth?	0.49
Physical Pain	Have you had painful aching in your mouth?	0.34
	Have you found it uncomfortable to eat any foods because of problems with your teeth or mouth?	0.66
Psychological Discomfort	Have you been self-conscious because of your teeth or mouth?	0.45

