(the study coordinator) will collect all tooth mobility measurements with the Periotest and means will be evaluated using non-parametric statistical analyses.

A Wilcoxon Rank Sum test for independent samples will be used to assess differences between groups for all the continuous variables with an $\alpha=0.05$ for irregularity index changes-Periotest measurements, VAS & OHIP-14 measures.

Salivary biomarker expression will be analyzed by ANOVA to assess differences between the four study groups at each time point. The study coordinator and principal investigator will perform statistical analyses.

VII. Timetable Table Timeline of Performance Goals:

Activity	Year 1-2014			Year 2-2015		
	X					
IRB, Staff training & preparation	X					
Subject Recruitment & Enrollment	X	X	X			
Final Assessments/Endpoints (17 weeks)				X		
Data Entry & Cleaning				X	X	X
Data analyses					X	X
Report writing						X

Expected Start Date: 2/1/2014

General Time Table

January 2014

Submit IRB for full board review

February 2014

Enrollment begins

Begin data collection for T0 time point in recruited subjects

August 2014

Initially recruited subjects complete study to final endpoint (T4)

June 2015

All consented subjects will have completed study

Data collection complete (N=20)

July 2015

Data analyses conducted

August 2015

Manuscript Preparation

➤ ***Expected Completion Date:*** August 2015

5) **Budget**

Patients will be responsible for covering the cost of orthodontic treatment in the University of Connecticut Orthodontics Clinic (either directly or with insurance). However, a deduction of \$400.00 on the standard orthodontic fees will be given to every patient enrolling in the research. The participants will receive this incentive in the form of \$100.00 at each research appointment completed until the maximum benefit is reached. If a participant is not compliant with the study protocol, he/she will be dismissed from the study and will not receive any further compensation. The same orthodontic procedures will be used for all subjects in this study regardless of study group.

Please see the attached budget detailing the study-specific costs.

6) **Dissemination**

The results of this research will be published in a peer-reviewed dental journal. In addition, this work is likely to be presented at national/international meetings.

References

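### The crowding entry criterion sets no minimum on the canine-to-canine irregularity index that is the denominator of the alignment outcome, so some precision for Hypothesis 3 may be lost

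*Combined protocol and SAP*

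**What the plan says.** The inclusion table under Enrollment asks for "At least 5mm of crowding in the mandibular arch". It does not say which teeth the crowding is counted over or how it is measured. The same table describes the dentition from first molar to first molar, so nothing there confines the arch to the front teeth. The pre-screen adds no irregularity threshold: "The initial clinical indicators of eligibility evaluated during the pre-screen are a healthy patient undergoing non-extraction treatment with good oral hygiene".

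The outcome is defined under Dental Model Analysis by a method based on Little's irregularity index on the mandibular cast: "Contact displacement will be measured in millimeters around the arch from canine to canine". Irregularity is then to "be evaluated based on percentage change over the 6-month evaluation period". Hypothesis 3 uses the same scale: "The percent change in alignment is greater in patients undergoing combined vibration-fixed appliance treatment compared to controls". Outcome Assessments lists alignment as secondary; the primary outcome is salivary biomarkers.

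Section VI gives the test: "A Wilcoxon Rank Sum test for independent samples will be used to assess differences between groups for all the continuous variables". It names irregularity index changes among the variables but does not repeat that they are percentages. Randomization is separate by sex only (section II). No section sets a minimum T0 index, stratifies on it, adjusts for it, or says what is done when it is close to zero.

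**The concern.** Entry and outcome differ in two ways. The region differs: mandibular arch against canine to canine. The measure differs too: crowding against summed contact displacement. Crowding behind the canines could satisfy the criterion as worded and add nothing to the index.

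Because the outcome is a percentage of T0, a small T0 index magnifies any error in reading either cast. The rank sum test gives such a subject the same weight as one whose percentage is well measured. What is at stake is the precision of the alignment comparison (Aim 3 and Hypothesis 3) in a trial of 40.

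**Working it through.** **Inputs from the protocol.** Two sexes × two arms × 10 = 40, so 20 against 20 for vibration versus control; α = 0.05; rank sum test; outcome as percentage change. The protocol gives no effect size, SD, power or cast-reading error for alignment, so there is no planned figure to reproduce. Everything below that needs such a figure is an assumption.

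**Step 1: error in one subject's percentage.** Let P = 100 × (T0 − T3)/T0, with independent reading errors of SD e (mm) on each cast and r = T3/T0, the share of irregularity remaining. The derivatives are 100r/T0 with respect to T0 and −100/T0 with respect to T3. By the delta method:

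SD(P) = 100 × e × √(1 + r²)/T0

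With an assumed 80% true reduction, r = 0.2 and √1.04 = 1.020:

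| T0 index | e = 0.3 mm | e = 0.5 mm |
|---|---|---|
| 1 mm | 30.6 points | 51.0 points |
| 2 mm | 15.3 | 25.5 |
| 5 mm | 6.1 | 10.2 |
| 8 mm | 3.8 | 6.4 |

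The ratio between two baselines depends on neither e nor r: a 2 mm subject is 5/2 = 2.5 times as noisy as a 5 mm subject. With a 60% reduction instead (r = 0.4, √1.16 = 1.077), the figures are 32 to 54 points at 1 mm and 6.5 to 11 points at 5 mm, so the pattern does not depend on the assumed reduction.

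The delta method is optimistic at very low baselines. In simulation with r = 0.4 and e = 0.3 mm, the 95% range of the observed percentage was −41 to 100 at 1 mm and 47 to 72 at 5 mm.

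**Step 2: effect on the planned test.** The rank sum test was simulated at 20 against 20, two-sided 0.05, 3,000 runs per setting. Assumptions: true reductions of 50% and 65%, between-subject SD 15 points, most baselines 5 to 10 mm, and a share of subjects at 0.5 to 2 mm.

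| Share at 0.5–2 mm | Power, e = 0.3 mm | Power, e = 0.5 mm |
|---|---|---|
| None | 82% | 76% |
| 10% (4 of 40) | 75% | 66% |
| 25% (10 of 40) | 65% | 51% |
| 50% (20 of 40) | 48% | 31% |

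A separate run of the same model, with an average of 2 of 40 at 0.5 to 2 mm, gave about 83% falling to 79% at e = 0.3 mm and 76% falling to 70% at e = 0.5 mm. If the low baselines are 2 to 4 mm rather than 0.5 to 2 mm, the loss at e = 0.3 mm is small: 82% to 81% with 2 of 40, and 78% with 10 of 40. Differences of about a point between runs are simulation error, since √(0.82 × 0.18/3,000) = 0.7 points.

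**Step 3: validity.** With no true difference, the rejection rate stayed between 4% and 6% in every setting of the table.

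**The case against.** The strongest objection is about size. The harm depends on how often a subject with 5 mm of crowding has an index near 1 mm, and nothing in the protocol says. If such subjects are rare, the loss is a few points of power for one of several secondary outcomes, in a pilot with no power target. The 48% and 31% figures need half the sample to have very low baselines. Two evaluators read the casts, and averaging their readings (which the plan does not specify) would reduce the error. All of this stands, and it sets the priority.

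A reader might infer that the alignment comparison is biased or its error rate inflated. The protocol does not support that. Baseline measures precede randomization, so low-baseline subjects fall to either arm by chance; ranking limits the pull of extreme percentages; and the simulated type I error is near 5%. A reader might also infer that the criterion deliberately counts crowding behind the canines, or that many such subjects will enter. The text permits the first without stating it, and is silent on the second.

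It can also be said that an arch-wide criterion suits the other outcomes: brackets run to the second premolars, and Periotest includes those teeth. An index minimum would narrow the whole trial for one secondary outcome. That is a real cost. Still, no section ties arch-wide crowding to the biomarker outcome, and the minimum can be added without removing the existing criterion.

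Finally, adjusting for T0 would stabilise the analysis without touching eligibility. That is right as far as it goes. It removes the unstable denominator, but a subject with almost no front irregularity still has little movement to show. The two measures complement each other.

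**Conclusion.** The mismatch holds on the text: entry does not guarantee any minimum of the quantity that forms the outcome's denominator, and no analysis rule covers a low value. The consequence is possible loss of precision for Hypothesis 3, not loss of validity. For an affected subject it is large: 31 to 51 points of error SD at 1 mm against 6 to 10 at 5 mm, assuming 0.3 to 0.5 mm cast error and an 80% reduction. For the comparison it is about 4 to 6 points of power if 2 of 40 have a T0 index of 0.5 to 2 mm, less if the low baselines are 2 to 4 mm, and more if low baselines are common. The error, effect and baseline distributions behind these figures are all assumed. Priority is low to moderate: the outcome is secondary, but the criterion cannot be repaired once subjects are enrolled.

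**What to change.** Add to the inclusion table a minimum canine-to-canine irregularity index on the mandibular cast. The sponsor should choose the value and state the reason; 5 mm is one option, but the existing 5 mm refers to a different measure and does not justify itself on this one. State also how crowding itself is measured.

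Read the index on the screening model where one exists. One is not guaranteed, because Enrollment and the screening text list models as one of several possible records, and the timetable places the first study impression at T0. Otherwise read the T0 cast before randomization; the timetable already confirms inclusion at that visit, and randomization follows the baseline measures. The cast would then have to be ready before allocation.

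In section VI, state the scale of the irregularity change and add an analysis of the T3 index adjusted for the T0 index, reported alongside the percentage change. This covers any low baselines that remain and needs no new data.

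The cost is an added entry line, one cast reading and one added analysis. An unknown share of otherwise eligible subjects would be excluded, including some with mixed front and rear crowding. With about 600 starts a year for 40 places this is probably manageable, though the protocol does not say how many of those starts meet the other criteria.

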Once recruited to the study and after baseline measures are taken at T0 by the study coordinator, the randomization will be performed. Since study groups will be subdivided by gender, separate randomization will be performed for males and females. Block randomization will be used. Based on gender, 20 opaque envelopes will be generated containing the group allocation (10 for the vibration study group, 10 for the non-vibration control group). At the time of randomization, the

subject will choose an envelope and disclose the group assignment. For subjects allocated to the vibration group, the study coordinator will provide detailed instructions as to how to operate the appliance and will instruct those subjects to use it for 20 minutes per day.

Timetable of Study Assessments

Assessment/ Visit	Screen	Baseline T0	Visit T1	Visit T2	Visit T3
Week	2d-to -6w	0	5-6	10-12	15-17
Consent	X				
Inclusion Criteria/ Confirm	X	X			
Alginate Impression		X	X	X	X
Randomization *		X			
Braces applied /bonded		X			
Vibration Appliance instructions**		X			
Saliva Collection		X	X	X	X
Clinical Data		X	X	X	X
Periotest		X	X	X	X
Pain Diary*** & OHIP 14		X	X	X	X***
Model Analysis		X	X	X	X
Record Adverse Effects		X	X	X	X

*Randomization before bonding

**For vibration group only- SC initially provides device and manufacturer's instructions.

*** Diary provided @ Baseline & visit T1, T1 to be collected on next visit.

III. Data Collection Procedures (See Study Timetable)

On the day of bonding (T0), prior to the placement of any appliances, baseline unstimulated whole saliva will be collected and Periotest will be performed on selected teeth in the mandibular arch. In addition, alginate model impressions will be taken. These procedures will be described in more detail in the next sections. Once baseline measures have been taken, the PI will perform the randomization and notify the study coordinator as to which group the subject is assigned to ("vibration treatment" or "no vibration"). The patients allocated to the vibration treatment group

will be provided with the AcceleDent appliance and instructed to use the 20 minutes per day according to the manufacturer's instructions.

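### The envelope is opened before bonding for no stated reason, which leaves an avoidable possibility of arm knowledge during bracket placement (minor, cheap to change)

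*Combined protocol and SAP*

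**What the plan says.** The order of events at T0 has to be put together from several places.

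- **Timetable of Study Assessments, footnote:** "Randomization before bonding". Both events fall in the T0 column.
- **II. Randomization Procedures:** "after baseline measures are taken at T0 by the study coordinator, the randomization will be performed". The "subject will choose an envelope and disclose the group assignment".
- **III. Data Collection Procedures:** "prior to the placement of any appliances, baseline unstimulated whole saliva will be collected and Periotest will be performed on selected teeth" in the lower arch. "In addition, alginate model impressions will be taken". After that, "the PI will perform the randomization and notify the study coordinator as to which group the subject is assigned to". The next paragraph describes treatment with or without vibration as what follows once fixed appliances are in place.
- **Enrollment** and **I. Standardized Orthodontic Treatment Protocol:** the patient's own provider does the bonding. Bracket type, the teeth bonded and the first archwire are the same for everyone.
- **Dental Model Analysis:** the two cast evaluators are the only people described as blinded.
- **Oral Health Quality of Life (OHQoL):** "The OHIP-14 (exhibit below) will be administered at each study visit". The timetable marks it at T0, in one row with the pain diary. It is not among the measures that section III names as preceding appliances and allocation.

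**The concern.** Under this order, three parties know the arm before bonding starts, and one of them is the subject in the chair. No text keeps the provider from learning it from the subject or the coordinator. Bracket position is operator work done at this visit, and it can influence early alignment, mobility and pain. One sentence in section I places the second archwire at T2, in which case the T0 set-up would carry through the T1 and T2 measurements. The same section also leaves wire timing to the provider, so those two statements need reconciling; this point does not depend on which prevails.

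Two smaller consequences follow. If bonding cannot be completed on the day, the subject has already used one of a fixed stock of envelopes and is a randomised subject without treatment. And OHIP-14 is self-reported and analysed as change over time. A T0 score given after the arm is known, or after brackets are on, would not be a clean baseline.

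**Working it through.** There is no plan figure to reproduce: the trial is described as a pilot, and section IV gives no power calculation. The check is mainly one of sequence, with a small illustration of the loss.

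**1. Who knows the arm at bonding**

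| Party | Knows the arm before bonding? | Source |
|---|---|---|
| Subject | Yes, opens the envelope | II |
| Principal investigator | Yes, performs the randomisation | III |
| Study coordinator | Yes, is notified | III |
| Bonding provider | Not stated; no blinding stated | Enrollment, I |
| Cast evaluators | Described as blinded | Dental Model Analysis |

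**2. Is there a reason to allocate before bonding?** Section III places treatment with or without vibration after appliance placement. Device instructions are a separate T0 item handled by the coordinator. No T0 step before or during bonding is described as differing by arm. No reason for the early point is given.

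**3. Which baselines are affected?** Saliva (the primary outcome), Periotest and impressions are explicitly taken before appliances and allocation. OHIP-14 sits in the baseline column, and the general rule puts randomisation after baseline measures. However, the specific list leaves it out, and its order within T0 is not stated.

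**4. Size of a bonding-day loss**

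- Counts: 2 genders × 2 arms × 10 = 40 subjects, and 2 × 20 = 40 envelopes, which agree.
- One loss is 1/10 = 10% of a gender-by-arm cell, or 1/20 = 5% of an arm.
- No failure rate is given, so a range is assumed. Expected losses are 40p, and the chance of at least one is 1 − (1 − p)^40:

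| Assumed p | Expected losses | Chance of at least one |
|---|---|---|
| 0% | 0 | 0% |
| 2.5% | 1 | 64% |
| 5% | 2 | 87% |
| 10% | 4 | 98.5% |

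- Detectable standardised difference (two-sided 0.05 and, as an assumption, 80% power; normal approximation): (1.960 + 0.842) × √(1/n₁ + 1/n₂).

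| Comparison | Detectable difference (SD) |
|---|---|
| 20 vs 20 | 0.886 |
| 19 vs 20 | 0.898 |
| 18 vs 18 | 0.934 |
| 10 vs 10 (one cell pair) | 1.253 |
| 9 vs 10 | 1.287 |

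One loss costs 0.012 SD at arm level and 0.034 SD between two cells. Precision is not the issue. What matters is that such losses fall after allocation and could differ by arm.

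**The case against.** The strongest reply is that allocating after baseline and before treatment is an ordinary sequence, and that the documents never say the provider is told the arm. This stands. A reader might infer that all 40 bondings are done by an operator who knows the arm. The text shows only that nothing prevents it.

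The room for bias at bonding is also limited. Brackets, bonded teeth and first archwire are fixed by protocol, and the Budget section says the same orthodontic procedures apply in both groups. What remains is mainly bracket positioning, and the documents give no size for an operator effect.

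The larger discretion lies in when to move to the next archwire, which comes after allocation under either order. Subjects stay aware of their arm, and so does the coordinator who takes the Periotest readings. This stands too: the change protects one step, not the trial.

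On OHIP-14, the general rule that randomisation follows baseline measures is the natural reading and probably covers it. A reader might infer from the list in section III that the T0 score is taken after disclosure. The documents do not show that; the gap is one of wording.

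Finally, bonding-day failure is hypothetical here, and section V keeps the data of withdrawn subjects. For a subject lost between envelope and bonding, however, those data would be T0 measures only.

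None of this supplies a reason for the early allocation, and the remaining exposure can be removed almost for free.

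**Conclusion.** The point holds as a minor, low-cost improvement. Allocation before bonding is explicit, three parties know the arm before brackets are placed, the provider is not protected from learning it, and the documents give no reason for the order. The consequence is an avoidable possibility of arm knowledge during bracket positioning, bearing mainly on secondary outcomes. The baseline of the primary outcome is secure.

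The loss component is 10% of a cell per subject, at an unknown rate and with a small precision cost (0.886 to 0.898 SD for one loss from an arm).

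The conclusion assumes that vibration need not be available before bonding. Section III implies this but gives no explicit start time, so a reader who concludes that vibration cannot begin earlier goes further than the text. It also assumes that the provider could learn the arm from the subject or coordinator at the chairside, which is plausible but undocumented.

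**What to change.** Reorder the T0 visit in the timetable footnote and in sections II and III:

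1. OHIP-14, saliva, Periotest and impressions.
2. Bonding and placement of the first archwire.
3. Envelope opened.
4. Device and instructions for the vibration arm.

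The footnote could read: *Randomization after bonding and placement of the first archwire, as the last step of T0 before device instructions.* Add OHIP-14 by name to the measures that section III lists as preceding bonding and allocation. With this order, a bonding not completed on the day is an exclusion before randomisation and uses no envelope.

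The cost is a re-ordering of steps within one visit and a few edits to the text, with no added visit, measurement or subject. The limit should be stated openly: providers and subjects remain unblinded at later visits, so discretionary archwire progression is not protected by this change.

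### No pain rating precedes bonding and disclosure of the arm, and the T0 OHIP-14 is not expressly placed before randomization, so change in pain and OHQoL lacks a secured pre-treatment reference (minor)

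*Combined protocol and SAP*

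**What the plan says.** The secondary outcomes in Outcome Assessments are "Changes in 1) tooth mobility, 2) change in alignment 3) changes in pain and OHQoL".

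**Pain.** Under Orthodontic Pain Assessment, diaries are handed out at T0, T1 and T2 for subjects "to record the level of orthodontic pain each evening for the first 7 days after each study visit", on a VAS from 1 to 10. A footnote to the Timetable of Study Assessments gives the diary only at Baseline and T1.

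**OHIP-14.** The OHQoL section says: "The OHIP-14 (exhibit below) will be administered at each study visit and the profile changes will be compared across time points". The timetable marks it at T0 to T3, in one row with the pain diary.

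**Order of events at T0.** Section II says that "after baseline measures are taken at T0 by the study coordinator, the randomization will be performed"; a timetable footnote puts randomization before bonding. Section III lists what is done before appliances are placed: "baseline unstimulated whole saliva will be collected and Periotest will be performed on selected teeth in the mandibular arch". It continues: "In addition, alginate model impressions will be taken". Neither a VAS rating nor OHIP-14 is in that list. Under section II the subject picks the envelope and reveals the assignment, and no sham device is described.

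**Analysis.** Section VI compares the groups on VAS and OHIP-14 measures by the Wilcoxon rank sum test at 0.05. It does not say whether scores or changes are tested, from what reference a change is taken, or whether baseline is adjusted for.

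**The concern.** An outcome named as a change needs a stated starting value. For pain there is none from before treatment: by the first diary evening the brackets and first archwire are in place, the subject knows the arm, and a vibration subject has the device. If change is instead taken between diaries, the reference is itself a post-allocation, unblinded score.

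For OHIP-14 the issue is order within a single visit. Consent, scheduling and the Baseline column do not say whether the form is completed before or after the envelope is opened and the braces are bonded. Its items ask about aching, eating and self-consciousness. Answers given after disclosure could reflect the known arm, and such a score would no longer serve as a clean baseline. A pre-treatment answer cannot be recovered once a subject has been bonded.

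**Working it through.** The plan states no figure on this point (section IV describes a pilot without a power calculation), so there is none to reproduce. The check is of timing, with three short calculations.

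**1. Ratings before treatment**
- Diaries as in Orthodontic Pain Assessment: 3 visits × 7 evenings = 21 ratings, 0 before bonding.
- Diaries as in the timetable footnote: 2 visits × 7 evenings = 14 ratings, 0 before bonding.
- OHIP-14: 4 administrations (T0 to T3), with the order of the first against allocation and bonding not stated.

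**2. What change between diaries would measure**

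Let mean control pain after T0, T1 and T2 be a0, a1 and a2. Suppose vibration lowers pain by d after every visit, giving a0 − d, a1 − d and a2 − d.
- Change from the T0 to the T1 diary, control: a1 − a0.
- The same change, vibration: (a1 − d) − (a0 − d) = a1 − a0.
- Difference between arms: 0, whatever d is.

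Comparing the diary scores themselves gives −d at each visit. So the choice of reference decides whether a constant effect is seen at all.

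**3. OHIP-14 completed after bonding (within-subject illustration)**

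The weights of the two physical-pain items are 0.34 and 0.66. One extra point on each adds 0.34 + 0.66 = 1.00 to a subscale running from 0 to 4, and takes 1.00 off that subject's later worsening. If the shift is s in both arms, the difference in mean change is (F_V − B_V − s) − (F_C − B_C − s) = (F_V − B_V) − (F_C − B_C), where F and B are follow-up and true baseline means. The shift cancels between arms. Only a shift that differs by arm would bias the comparison, and the documents give no basis for sizing one.

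**4. What a baseline could add in precision**

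Inputs: 40 subjects, 20 per arm. Assumptions: no dropout, two-sided 0.05, 80% power, normal approximation, and a baseline-to-follow-up correlation r that the documents do not give.
- Follow-up scores only: (1.960 + 0.842) × √(2/20) = 0.89 SD. With the rank test's efficiency of 0.955: 0.886/√0.955 = 0.91 SD.
- Baseline as covariate: 0.886 × √(1 − r²).
- Raw change score: 0.886 × √(2(1 − r)).

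| r | Covariate (SD) | Raw change (SD) |
|---|---|---|
| 0.3 | 0.85 | 1.05 |
| 0.5 | 0.77 | 0.89 |
| 0.7 | 0.63 | 0.69 |

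A covariate lowers the detectable difference at every r shown. A raw change score improves on follow-up scores alone only if r exceeds 0.5.

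**The case against.** **The pain comparison needs no baseline.** Hypothesis 4 is a comparison with controls, and section VI tests VAS between groups. Randomization makes that valid as it stands. The Background also expresses interest in how pain develops over successive visits, which repeated diaries serve, and pain caused by the appliance has no value before the appliance exists. All of this stands. It does not say what reference the named change uses, and the cancellation above shows that the answer matters.

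**OHIP-14 is already a baseline measure.** It is scheduled under Baseline T0, and randomization is said to follow the baseline measures, so the natural reading is that the form comes first. The section III list is weak evidence to the contrary: the matching sentence for T1 to T3 also names only saliva, Periotest and impressions, although the questionnaires are plainly scheduled then. This also stands. What remains is that no sentence expressly sets the order, and the shared row cannot, because its T0 mark also covers a diary completed after bonding.

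**Row order.** A reader might infer a post-bonding OHIP-14 from its place below randomization and bonding in the timetable. The inference fails: saliva and Periotest are printed below those rows too, yet section III takes both before any appliance.

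**Small gain for VAS.** Subjects are healthy and free of active oral lesions, so most should start near the scale floor, where a baseline explains little later variation. This is a fair expectation, though the documents give no data on it.

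**Conclusion.** The point holds as a minor one. No VAS rating precedes bonding and disclosure of the arm (0 of 21, or 0 of 14), so change in pain has no pre-treatment reference, and change between diaries would rest on a post-allocation value that could hide a constant effect. For OHIP-14 the gap is an unstated order, not a missing assessment; it matters because subjects know their arm.

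A reader might go further and infer that the pain analysis is invalid, or that OHQoL is biased between arms. The documents support neither. The randomized comparison of diary scores stands without a baseline, a bonding effect common to both arms cancels, and the 1.00-point shift is only a within-subject illustration.

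The size of the benefit depends on r, which is assumed: with a covariate, the detectable difference would fall from 0.89 SD to between 0.85 SD (r = 0.3) and 0.63 SD (r = 0.7), with 20 per arm and no dropout. For VAS the gain is likely at or below the small end of that range. These are secondary outcomes in a 40-subject pilot.

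**What to change.** - In section III, add OHIP-14 and one VAS rating to the T0 measures completed before randomization and bonding.
- In the timetable, list OHIP-14 and the pain diary in separate rows.
- In Outcome Assessments and section VI, state the reference value for change in pain and in OHQoL. Use the T0 values as covariates, for example in a rank-based ANCOVA, and do not rely on raw change scores.
- Reconcile the diary schedule between the timetable footnote (Baseline and T1) and Orthodontic Pain Assessment (T0, T1 and T2).

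The cost is a few minutes at a visit already attended, one extra VAS line and some wording changes. The drawback is a little added burden at T0 for what may be a small return on the VAS side.
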